10.2 Adverse Event Monitoring and Documentation

10.2.1 Event Monitoring

Monitoring for adverse events will begin with the start of the exemestane and continue through and including 28 calendar days after the last dose of exemestane.

10.2.2 Event Documentation

Adverse events occurring after the initiation of exemestane treatment through and including 28 calendar days after the last dose must be documented. Refer to Section 6.1.1 for a list of expected toxicities of exemestane and Appendix IV for a list of expected toxicities for the ICB therapy.

Since a key outcome parameter of this study is to characterize the toxicities of exemestane in combination with an FDA approved immune checkpoint inhibitor in this patient population, adverse event documentation requirements will be

determined based on grade, expectedness and relationship to study therapy as follows:

	CTCAE Grade 1	CTCAE Grade 2		CTCAE Grade 3		CTCAE Grade 4 and 5
	Expected or Unexpected	Expected	Unexpected	Expected	Unexpected	Expected or Unexpected
Unrelated Unlikely	Not required	Not required	Not required	Not required	Required	Required
Possible Probable Definite	Not required	Not required	Required	Required	Required	Required

In addition any event meeting the definition of a serious adverse event (SAE) regardless of attribution that occurs during this period will be documented in the source document and recorded in OnCore.

After the end of treatment visit, monitoring for adverse event will become less frequent based on the schedule in Section 9 and only events at least possibly related to study treatment (based on the table above) will be documented upon knowledge.

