1.2 Secondary Objectives

- To determine the toxicity profile of daily exemestane in combination with immune checkpoint blockade therapy in this patient population.
- To estimate the disease control rate, progression-free survival (PFS), and overall survival (OS) of exemestane for up to 1 year from study enrollment in post-menopausal women with previously treated advanced NSCLC.
- To estimate quality of life during study treatment and for one month following discontinuation of study treatment.

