6.1.1 Exemestane Expected Toxicity

Based on extensive use in post-menopausal women with breast cancer as sourced through IBM Micromedex® available through the University of Minnesota Libraries:

In general, exemestane is well tolerated at this dose when given long term to post-menopausal women with breast cancer. It is thought that adding exemestane to ongoing immune checkpoint blockade the risks profile for neither drug will be different.

Rare, but potentially serious side effects

Bone loss. Exemestane lowers the level of estrogen in the body and may reduce bone mineral density (BMD) over time, possibly increasing the risk of bone fracture. A DEXA scan will be done at baseline, if none performed in the previous 12 months and every 12 months while receiving exemestane.

Chest pain, heart failure, or stroke. A small number of women had chest pain, heart failure, or a stroke while taking exemestane

Occurring in less than 1 out of 100 women

Gastric ulcer

Cholestatic hepatitis, hepatitis

Common side effects (occurring in 10 or more out of 100 women)

- hot flashes
- fatigue
- joint pain
- headache
- insomnia
- increased sweating
- depression
- feeling anxious
- upset stomach
- difficulty breathing
- hair loss or thinning
- an increase by a blood test of a liver enzyme (alkaline phosphatase) that may indicate a bone disorder or liver disease

Use of estrogens (such as hormone replacement therapy or HRT) and phytoestrogen supplements (such as black cohosh) to relieve the menopausal like side effects are prohibited during exemestane treatment.

Only post-menopausal women are enrolled in this study as taking exemestane during pregnancy is known to cause birth defects and/or miscarriages.

Refer to the prescribing information for additional details.

We do not expect any difference in the toxicity profile of exemestane when it is added to an ongoing treatment with anti-PD1 or anti-PDL1 antibody treatment. There are ongoing clinical trials in breast cancer using the combination of hormone therapy and an immune checkpoint blockade.

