13.1 Study Design, Objectives and Endpoints

The goal of this phase II study is to estimate the probability of response after treatment of exemestane in post-menopausal women with advanced non-small cell lung cancer progressing while on immune checkpoint blockade. The primary endpoint of treatment response will be assessed at 6 weeks after the start of treatment using RECIST criteria. Secondary endpoints include the proportion of toxicities through 30 days after the last dose or start of new treatment as described in Section 10.2.2, disease-control as measured by response duration, progression-free and overall survival through 12 months from study enrollment and quality of life scores as measured by PROMIS-29 at baseline, every 3 weeks during treatment and at the end of treatment visit. The primary endpoint of response will be evaluated using a two-stage design.

Stage 1 will enroll 10 patients. If 2 or more patients have an objective response after completion of stage 1, an additional 19 patients will be enrolled in stage 2 for a total of 29 patients. If the total number of patients responding is 4 or greater, the treatment will be considered worthy of further investigation.

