13.3 Statistical Analysis

The primary endpoint of response will be estimated with a simple proportion and a 95% confidence interval. The secondary endpoints of survival and progression-free survival will be estimated with Kaplan-Meier curves. Disease control will be assessed with descriptive statistics and plots such as medians, ranges, interquartile ranges and box-plots. Toxicities will be assessed with descriptive statistics and plots such as simple proportions and bar graphs. Quality of life scores, as measured by PROMIS, will be evaluated descriptively at baseline, every 3 weeks during and at the final visit using medians, ranges, interquartile ranges and boxplots to look for trends in various areas measured by PROMIS. Analysis of correlative objectives will involve assessment of associations of baseline measurements of five biomarkers from tumor tissue and clinical outcome. Biomarkers will be evaluated by evaluation of quartiles with subsequent dichotomization and then comparison by response using a Chi-square test or Fisher's exact test depending on sample size. Evaluation of biomarkers is primarily descriptive and will be used in the planning of future studies both for selection criteria and validation. Six biomarkers from blood will similarly be assessed; however, these measurements will be assessed at individual post-treatment time-points as well. If warranted, repeated measures analyses may be used to look at measurements over time. There is currently no plan to demonstrate that the biomarkers could be used as surrogate endpoints but rather if associations exist for future evaluation.

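### The adverse-event table behind the toxicity endpoint does not require Grade 1 or expected Grade 2 events even when related, and the endpoint is not labelled as limited in that way

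*Combined protocol and SAP*

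**What the plan says.** The first secondary objective in Section 1.2 is "To determine the toxicity profile of daily exemestane in combination with immune checkpoint blockade therapy in this patient population". Section 13.1 makes the endpoint "the proportion of toxicities through 30 days after the last dose or start of new treatment as described in Section 10.2.2". Section 12.2 has toxicity graded by CTCAE, with attribution and expectedness assigned, and states no minimum grade. Section 13.3 adds "Toxicities will be assessed with descriptive statistics and plots such as simple proportions and bar graphs".

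Section 10.2.2 first makes documentation of adverse events obligatory from the start of exemestane to 28 days after the last dose. It then gives the purpose, "Since a key outcome parameter of this study is to characterize the toxicities of exemestane in combination with an FDA approved immune checkpoint inhibitor", and says that the requirements are "determined based on grade, expectedness and relationship to study therapy as follows". The table that follows reads:

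| Attribution | G1 any | G2 expected | G2 unexpected | G3 expected | G3 unexpected | G4-5 any |
|---|---|---|---|---|---|---|
| Unrelated, unlikely | no | no | no | no | yes | yes |
| Possible, probable, definite | no | no | yes | yes | yes | yes |

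(yes = required, no = not required.)

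Serious adverse events are recorded whatever their attribution. After the end-of-treatment visit, "only events at least possibly related to study treatment (based on the table above) will be documented upon knowledge". For expectedness, 10.2.2 points to Section 6.1.1 for exemestane and Appendix IV for the checkpoint inhibitors (ICB). Section 10.1 notes that the word drug means exemestane, and defines attribution relative to the study drug.

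**The concern.** The table is presented as serving the aim of characterising the combination's toxicity, yet it leaves optional the grades at which an oral aromatase inhibitor would be expected to show most of its effects. Section 6.1.1 lists 12 exemestane effects as affecting at least 10 in 100 women. Being listed, they would ordinarily count as expected. Section 2.3 describes the commonest events in advanced breast cancer as mild to moderate.

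A simple proportion built from the required records would therefore miss related Grade 1 and expected Grade 2 events. Optional does not mean forbidden, so some sites may record them and others not, and the resulting low-grade counts could not be interpreted. What is at stake is how far the report can answer the first secondary objective, and whether a reader would take the proportions as all-grade rates.

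**Working it through.** The plan states no figure on this point, so there is none to reproduce. The check is a reading of the table, followed by an illustration of scale.

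**1. Cells.** Two attribution rows by six columns give 12 cells. Not required: 4 in the unrelated/unlikely row plus 2 in the related row, 6 in all. The two related cells are Grade 1 (any) and Grade 2 expected.

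**2. Internal conflict.** The opening obligation in 10.2.2 has no grade limit, while the table exempts half its cells. Both cannot govern. The sentence introducing the table suggests that the table does.

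**3. Other routes into the data.**
- Serious events are recorded at any grade.
- Section 9.1 schedules symptom and toxicity notation at baseline, every 3 weeks and at end of treatment, and the daily log has a side-effect column. No section says that these entries are graded or enter the toxicity analysis.
- PROMIS-29 has fatigue, sleep, anxiety and depression domains, which match 4 of the 12 effects in 6.1.1, and it has pain items. It has no item for hot flushes, sweating or nausea, and its scores are not CTCAE-graded or attributed.

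**4. Grade 3.** Under 10.1, attribution is to exemestane, and 10.4 also glosses study treatment as exemestane. An expected Grade 3 ICB toxicity judged unrelated or unlikely therefore falls in a not-required cell. It is still captured if it is serious, or if it is pneumonitis, colitis, nephritis, myocarditis or hepatitis (10.3). Immune-mediated rash and adrenal insufficiency, for example, are listed in Appendix IV for at least one agent and are not among the five. The phrase study therapy in 10.2.2 blurs this.

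**5. Scale (illustration).** Inputs: N = 29 (Section 13.1) and the early breast cancer exemestane rates p in Section 2.3. The share g of events that are Grade 1-2 is my assumption, run from 70% to 100%. I also assume that the rates carry over and that every such event is judged related and expected. Events expected = N x p. Events the table requires = N x p x (1 - g).

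| Event | p | N x p | g = 70% | 80% | 90% | 100% |
|---|---|---|---|---|---|---|
| Hot flushes | 21.2% | 6.15 | 1.84 | 1.23 | 0.61 | 0 |
| Fatigue | 16.1% | 4.67 | 1.40 | 0.93 | 0.47 | 0 |
| Joint pain | 14.6% | 4.23 | 1.27 | 0.85 | 0.42 | 0 |

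For hot flushes at g = 80%: 29 x 0.212 x 0.20 = 1.23, a proportion of 0.212 x 0.20 = 4.2%. At the lower advanced-disease rates, hot flushes (13%) give 29 x 0.13 = 3.77, of which 3.77 x 0.30 = 1.13 are required at g = 70%. Fatigue (8%) gives 29 x 0.08 = 2.32, of which 2.32 x 0.30 = 0.70 are required. With only the 10 Stage 1 patients, hot flushes at 21.2% give 10 x 0.212 = 2.1 cases.

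**6. Window.** Sections 10.2.1, 10.2.2 and 10.4 run routine capture to day 28. Sections 12.2 and 13.1 run the endpoint to day 30. The gap is 30 - 28 = 2 days.

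**The case against.** The best defence is that the restriction is deliberate and that the endpoint matches it. Section 13.1 points to 10.2.2, so the endpoint can be read as counting exactly what the table requires. Exemestane is approved, Section 2.5 calls its profile well established, Section 6.1.1 expects no change when it is added to an ICB, and no IND is needed. This largely stands: limited capture is a defensible choice. It does not rescue the text, because 1.2, 12.2 and 13.3 never say that the profile is limited by grade, and the opening of 10.2.2 says the opposite.

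Three further arguments stand in part. PROMIS-29 does follow several of the listed symptoms, though not as adverse events. The electronic case report forms are not among the documents and may collect more. In a single arm already on an ICB, low-grade counts would separate the agents poorly: Appendix IV gives ICB fatigue as 20% to 71%, 49% and 52%, against 8% to 16.1% for exemestane in Section 2.3.

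A reader might infer that the proportions will be understated by a known amount, for instance hot flushes falling from about 21% to about 4%. The documents do not support that. Section 2.3 gives no grade split, its mild-to-moderate remark covers only advanced disease, and a proportion is understated only if it is presented as all-grade. A reader might also infer that safety monitoring is weakened. It is not: the Section 13.4 rules count Grade 4-5 related events and Grade 3-5 events of the five immune types, all of which are captured. Nor does the gap justify making all six optional cells required, since unrelated Grade 1-2 events on an ICB background would add much data entry for little information.

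**Conclusion.** The point holds as a minor one. Followed as written, the toxicity proportions would omit or unevenly capture Grade 1 and expected Grade 2 events related to exemestane. They would also omit a narrow class of expected, non-serious Grade 3 ICB toxicities judged unrelated to exemestane. The direction is clear, but the size cannot be derived from the documents, and the counts shown rest on an assumed grade share and on breast cancer rates carried over to another population. The conclusion also assumes that effects listed in 6.1.1 and Appendix IV are classed as expected at low grade. Section 10.1 leaves some judgement there, on severity and on the population studied. The primary endpoint, the go/no-go rule, serious events, Grade 4-5 capture and the stopping rules are unaffected. The 2-day window mismatch is real but small: table-required related events after the end-of-treatment visit, and related serious events after day 28, are still documented when they become known.

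**What to change.** Choose one of two routes.

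- **Widen capture.** In the 10.2.2 table, make three cells required: Grade 1 and expected Grade 2 in the possible/probable/definite row, and expected Grade 3 in the unrelated/unlikely row. Not-required cells fall from 6 to 3, all of them unrelated/unlikely Grade 1-2. The report should say that those are not collected.
- **Label the endpoint.** Keep the table, state in 1.2, 12.2 and 13.1 that the toxicity endpoint covers only the events it requires, and report it under that label.

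On either route, reconcile the opening obligation of 10.2.2 with the table, align the term study therapy there with study drug in 10.1, and bring the 28-day capture period (10.2.1, 10.2.2, 10.4) and the 30-day endpoint window (12.2, 13.1) into agreement.

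The first route costs some extra case report form entries for at most 29 patients (10 if Stage 2 is not opened), drawn from toxicity already noted every 3 weeks, with no new visits or procedures. Low-grade events such as fatigue would remain hard to attribute without a comparator. The second costs only a text amendment, but the low-grade profile then goes unreported.

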10.3 Stopping Rule Events

For the purpose of this protocol any Grade 4 or 5 treatment related event and any Grade 3, 4, or 5 immune related adverse event (pneumonitis, colitis, nephritis, myocarditis or hepatitis) will be considered excess toxicity per Section 13.4 and be reported as a stopping rule event using the Event Form found in OnCore.

Events that count toward an early study stopping rule do not necessarily constitute an event requiring expedited reporting and should only be reported as such if they meet the criteria found in Section 10.5.

10.4 SAE and Death Documentation

The reporting period for this study is from initiation of study treatment (exemestane) through and including 28 days after the last dose of exemestane. However, after this time point, the investigator must report upon knowledge any study treatment related meeting the definition of a serious adverse event (SAE) using the MCC SAE Report Form in OnCore.

Deaths, including due to disease, within the follow-up period will be recorded as an SAE. Deaths due to disease should be recorded as a Grade 5 “Neoplasms benign, malignant and unspecified (including cysts and polyps) – Other (Progressive Disease).

In addition, upon knowledge, the death date and cause must be reported in the patient follow-up tab in OnCore using the comment field in the survival status section to record the cause.

10.5 MNCCTN Required Reporting To the MCC CTO

The following events are to be reported to the Masonic Cancer Center Clinical Trials Office in an expedited manner based on the table below. In addition, the Network site is responsible for reporting to their local IRB as required.

Event Type	Reporting Timeframe	Form in OnCore to Use
Any event meeting the definition of serious and all patient deaths	Within 24 hours of knowledge	SAE Report Form
Stopping Rule Events	Within 24 hours of knowledge	Stopping Rule Event Form
Major Deviations, as defined in Section 10.1.	Within 5 working days of knowledge	Deviation Report Form

The MCC CTO is responsible for reporting qualifying events to the UMN IRB, Pfizer and the MMC SAE coordinator per Section 10.6.

10.6 Required Reporting By the CTO to UMN IRB, Pfizer, and MCC SAE Coordinator

Agency reporting to	Criteria for reporting	Timeframe	Form to Use	Submission address/ fax numbers
U of MN IRB	Unexpected Death, Information that indicates a new or increased risk, or a safety issue.	5 Business Days	Ethos Reportable New Information (RNI)	Via Ethos and/or Oncore
	Deviations that occur at MCC	5 Business Days	OnCore Deviation Form and Ethos RNI	
Pfizer	Abstracted from Pfizer's Safety Reporting Reference Manual for Investigator-Initiated Research (IIR) Interventional Studies Using the criteria for Mature Anti-Cancer Products- SAEs are reported only if they are: 
 Deaths that occur during the study reporting period SAE's that occur during the study period and are assessed by the investigator as both related to exemestane and unexpected Any related SAE that occur after the study reporting period that the investigator becomes aware of Refer to the Safety Reporting Manual found as an attachment under this study in OnCore 	immediately upon awareness, if the SAE is fatal or life-threatening – regardless of the extent of available information or within 24 hours of first awareness of the SAE, if the SAE is not fatal or life-threatening	Attached in OnCore under this study	Refer to Reportable Event Fax Cover Sheet – attached in OnCore under this study
Masonic Cancer Center SAE Coordinator	Events that meet the criteria of an early study stopping rule	At time of reporting	Event Form	SAE Coordinator [contact]

11 Study Data Collection and Monitoring

11.1 Data Management

This study will collect regulatory and clinical data using University of Minnesota CTSI's instance of OnCore® (Online Enterprise Research Management Environment).

The Oncore database resides on dedicated secure and PHI compliant hardware located in the University of Minnesota (UMN) datacenter (WBOB) All the data servers are managed by the Academic Health Center – Information Systems (AHC-IS) virtual servers which utilize clustered infrastructure to provide real-time failover of virtual servers. All relevant AHC IS procedures related for PHI compliant servers (as required by the Center of Excellence for HIPAA Data) apply to Oncore databases.

The integrated data will be stored in PHI compliant servers managed by AHC IS with access given to those authorized users in the Clinical and Translation Science Institute Informatics team (CTSI BPIC and MCC CISS). The informatics team will grant the IRB approved study team members access to data.

Additional data about correlative laboratory samples generated by the Masonic Cancer Center Translational Therapy Laboratory (TTL) from the protocol-directed correlative research samples is stored in their Laboratory Information Management System (LIMS).The LIMS database application is also stored on a production server located in the UMN datacenter (WBOB) and is managed by the Academic Health Center

Key study personnel are trained on the use of OnCore and will comply with protocol specific instructions embedded within the OnCore.

11.2 Case Report Forms

Participant data will be collected using protocol specific electronic case report forms (e-CRF) developed within OnCore based on its library of standardized forms. The e-CRF will be approved by study's Principal Investigator and the Biostatistician prior to release for use. The Study Coordinator or designee will be responsible for registering the patient into OnCore at time of study entry, completing e-CRF based on the patient specific calendar, and updating the patient record until patient death or end of required study participation.

11.3 Data and Safety Monitoring Plan (DSMP)

The study's Data and Safety Monitoring Plan will be in compliance with the University of Minnesota Masonic Cancer Center's Data & Safety Monitoring Plan (DSMP), which can be accessed at <http://z.umn.edu/dmsp>

For the purposes of data and safety monitoring, this study is classified as moderate-risk (Phase II). Therefore the following requirements will be fulfilled:

- Twice yearly review by the Masonic Cancer Center Data and Safety Monitoring Council (DSMC) with the understanding the Cancer Protocol Review Committee (CPRC) may require more frequent reporting.
- The PI will comply with at least twice yearly monitoring of the project by the Masonic Cancer Center monitoring services.
- The PI will oversee the submission of all reportable adverse events per the definition of reportable in Section 10.6 to the Masonic Cancer Center's SAE Coordinator, the University of Minnesota IRB and Pfizer.

11.4 Investigational New Drug (IND) Assessment

A commercial formulation of Exemestane will be provided by Pfizer for the purposes of this study. In addition was determined that this study meets all conditions of the exemption criteria found in 21 CFR 312.2. No IND application is required for this study.

11.5 Monitoring

The investigator will permit study-related monitoring, audits, and inspections by IRB, government regulatory bodies, and University of Minnesota compliance groups. The investigator will make available all study related documents (e.g. source documents, regulatory documents, data collection instruments, study data, etc.). The investigator will ensure the capability for inspections of applicable study-related facilities (e.g. pharmacy, diagnostic laboratory, etc.) will be available for trial related monitoring, audits, or regulatory inspections.

